4.7 Research procedure

4.7.1 Patient selection and data collection

The study population will include those patients with symptomatic gall stones who will be treated by laparoscopic cholecystectomy in No.(1) Military Hospital (700 bedded) and will not be met the exclusion criteria. Complete history will be taken including patient's identification, presenting symptoms, past medical and past surgical history. Thorough physical examination including general and abdominal examination will be performed. Investigations including liver function test, complete blood picture, urea, creatinine, viral serology for preoperative assessment will be done. Abdominal sonography will be carried out. The results will be recorded in the proforma.

After selection of the patients by inclusion and exclusion criteria, eligible patients will be counseled by the author about nature of disease, type of operation to be performed and possible complications. If the patient agrees to participate, a written informed consent will be obtained. The participants will be randomly allocated by block randomization method. Method A conventional laparoscopic cholecystectomy (CLC) will be done for control group and Method B two ports plus one puncture laparoscopic cholecystectomy (TPPOP LC) will be done for study group.

4.7.2 Preoperative preparation

The patients will be reviewed by anesthetist for preoperative assessment. General anesthesia will be required for both types of procedure. All patients will be entailed fasting for 6 hours. Prophylactic antibiotics will be given as intravenous ceftriaxone 1G at induction of anesthesia in both methods. If the patient has cephalosporin hypersensitivity, fluoroquinolones group like levofloxacin 500mg will be given. A nasogastric tube will be inserted at induction of anaesthesia to decompress the stomach in both study groups. The patient will be asked to void urine immediately prior to surgery. The patient will be placed in supine position in both study groups (**Fig 10**). The entire abdomen will be cleaned and draped in standard sterile fashion.

[figure not shown]

Figure 10. Operation table set up for laparoscopic cholecystectomy (Kumar et al, 2017)

4.7.3 Apparatus and instruments

These will include laparoscopic 30° telescope, video camera, camera control unit, light source, HD monitor, rapid flow insufflator, electro surgical unit, suction irrigation device and trocars (two 10 mm trocars and two 5 mm trocars for CLC and one 10 mm trocar, one 5 mm trocar for TPPOP LC), laparoscopic instruments, 2.3 mm alligator grasper, 5mm clip applier and specimen retrieval bags (**Fig 11 & 12**).

Figure 11. Laparoscopic instruments and apparatus for CLC

Figure 12. Laparoscopic instruments and apparatus for TPPOP LC

4.7.4 Procedures in conventional laparoscopic cholecystectomy

Step 1. A 10 mm subumbilical incision will be made and the first 10 mm trocar will be introduced by open Hasson technique (**Fig 13**).

[figure not shown]

Figure 13. Insufflation with open Hasson technique

Step 2. Carbon dioxide pneumoperitoneum will be created and maintain at 12 mm Hg. Video telescope will be inserted from subumbilical port and will assess the pathological site and the visible portion of the whole intra-abdominal organs.

Step 3. The patient will be placed in reverse Trendelenburg position and the operation table will be tilted 15° left laterally. Three other working ports will be inserted under vision via video scope. Another 10 mm trocar will be placed in the subxiphoid epigastric region, a 5 mm trocar will be placed in the right subcostal midclavicular line, and another 5 mm trocar will be placed in the right subcostal anterior axillary line location (**Fig 14**).

[figure not shown]

Figure 14. Trocars placement for conventional laparoscopic cholecystectomy

Step 4. The fundus of the gallbladder will be grasped with a non-traumatic forceps and pushed upwards and cranially to get good exposure. Calot's triangle will be displayed. Then cystic duct, cystic artery, common hepatic duct and common bile duct will be identified (**Fig 15**).

[figure not shown]

Figure 15. Grasping fundus and hartmann's pouch of gallbladder by conventional graspers

Step 5. A Maryland dissector will be used to clear the peritoneum over the infundibulum and cystic duct. The cystic duct will be clearly identified as it exits the infundibulum of the gallbladder and traverses toward the common bile duct. Once the peritoneum overlying the cystic duct is opened, the cystic duct will be cleared of its adventitial attachments circumferentially. Retracting the infundibulum toward the patient's left facilitates dissection of the lateral side of the cystic duct. The infundibulum will be again retracted to the patient's right and the triangle of Calot will be entered. An adequate segment of cystic duct will be cleared. Then cystic duct will be divided between haemoclips (**Fig 16**).

[figure not shown]

Figure 16. Dissection of cystic duct and cystic artery

Step 6. The cystic artery will be identified and cleared of surrounding attachments. When this has been verified, the cystic artery will be divided in continuity between clips.

Step 7. The infundibulum of the gallbladder will be retracted anteriorly allowing the gallbladder to be dissected from the liver bed using cautery and blunt or sharp dissection (**Fig 17**).

[figure not shown]

Figure 17. Liver bed after gallbladder dissection

Step 8. Then gallbladder will be placed into a specimen retrieval bag and removed through the subxiphoid port. If the gallbladder is exceedingly large, full of gallstones, or contains large stones, it may not be possible to safely remove the gallbladder. Options include crushing the stones inside the gallbladder with a clamp, removing many stones/stone fragments to help decompress the gallbladder, and/or enlarging the port incision (**Fig 18**).

[figure not shown]

Figure 18. Gallbladder specimen with multiple gallstones

Step 9. Once the gallbladder is removed, the liver bed will be examined to be sure there is no bleeding or bile leakage.

Step 10. Two 10 mm incisions will be closed at the fascial level with non-absorbable sutures. All skin incisions will be closed with non-absorbable sutures.

4.7.5 Procedures in two ports plus one puncture laparoscopic cholecystectomy

Step 1. A 10 mm subumbilical incision will be made and the first 10 mm trocar will be introduced by open Hasson technique (**Fig 19**).

Figure 19. Insufflation with open Hasson technique

Step 2. Carbon dioxide pneumoperitoneum will be created and maintain at 12 mm Hg. Video telescope will be inserted from subumbilical port and will assess the pathological site and the visible portion of the whole intra-abdominal organs.

Step 3. The patient will be placed in reverse Trendelenburg position and the operation table will be tilted 15° left laterally. The working 5 mm port will be inserted under vision via video scope and will be placed in the subxiphoid epigastric region (**Fig 20**).

[figure not shown]

Figure 20. 5 mm trocar insertion at subxiphoid epigastric region

Step 4. A 2.3 mm alligator grasper will be punctured below the right costal margin under vision via video scope (**Fig 21**).

[figure not shown]

Figure 21. Alligator grasper (2.3 mm) puncture below right costal margin

Step 5. The Hartmann's pouch of the gallbladder will be grasped with a 2.3 mm alligator grasper to get good exposure. Calot's triangle will be displayed. Then cystic duct, cystic artery, common hepatic duct and common bile duct will be identified (**Fig 22**).

[figure not shown]

Figure 22. Positioning laparoscopic instruments and grasping gallbladder by 2.3 mm alligator grasper

Step 6. A Maryland dissector will be used to clear the peritoneum over the infundibulum and cystic duct. The cystic duct will be clearly identified. Once the peritoneum overlying the cystic duct is opened, the cystic duct will be cleared of its adventitial attachments circumferentially. Retracting the infundibulum toward the patient's left facilitates dissection of the lateral side of the cystic duct. The

infundibulum will be again retracted to the patient's right and the triangle of Calot will be entered. An adequate segment of cystic duct will be cleared. Haemoclips will be applied to cleared segment of cystic duct by 5 mm clip applier, and then cystic duct will be divided between haemoclips (**Fig 23**).

[figure not shown]

Figure 23. Dissection of cystic duct and cystic artery

Step 7. The cystic artery will be identified and cleared of surrounding attachments. When this has been verified, the cystic artery will be divided in continuity between clips after applying with 5 mm clip applier (**Fig 24**).

[figure not shown]

Figure 24. Metallic clips applied by 5mm clip applier

Step 8. The infundibulum of the gallbladder will be retracted anteriorly by 2.3 mm alligator grasper allowing the gallbladder to be dissected from the liver bed using cautery and blunt or sharp dissection (**Fig 25**).

[figure not shown]

Figure 25. Liver bed after gallbladder dissection

Step 9. Then gallbladder will be placed into a specimen retrieval bag and removed through the 10 mm subumbilical port. This will be removed under vision via video telescope from 5 mm port. If the gallbladder is exceedingly large, full of gallstones, or contains large stones, it may not be possible to safely remove the gallbladder. Options include crushing the stones inside the gallbladder with a clamp, removing many stones/stone fragments to help decompress the gallbladder, and/or enlarging the port incision (**Fig 26 & 27**).

[figure not shown]

Figure 26. Gallbladder placement into a specimen retrieval bag

Figure 27. Gallbladder specimen with multiple gallstones

Step 10. Once the gallbladder is removed, the liver bed will be examined to be sure there is no bleeding or bile leakage.

Step 11. 2.3 mm alligator grasper will be removed and this punctured site will be covered with adhesive plaster only. 10mm subumbilical incision will be closed at the fascial level with non-absorbable sutures. All skin incisions will be closed with non-absorbable sutures.

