Bile duct injury is a serious complication which threatens the patient's safety. To minimize it, complete exposure and dissection of 'the critical view of safety' is strongly recommended before clipping or dividing the cystic structures. The critical view is best ensured by using 3 instruments, which enables both attainment of sufficient operative vision and bimanual manipulation. While dissecting during fewer port number and smaller size procedures, the 'best practice' approaches recommended for multiport cholecystectomy, including dynamic traction of the fundus of the gallbladder, dynamic lateral retraction of the gallbladder infundibulum, and identification and maintenance of the 'critical view' of the cystic duct and artery to avoid inadvertent injury to the common bile duct or hepatic arteries, should be followed (Ayman et al, 2013). Many researchers reported two ports LC can provide the critical view of safety conveniently, can maintain the principles of laparoscopic triangulation, and can preserve the fundamentals of laparoscopy such as operating ergonomics, surgical dexterity, and visualization of the surgical field (Adrian et al, 2013). According to the systematic review two ports LC; the two most common methods of two ports LC involve the insertion of two ports at umbilical and epigastric region and gallbladder anchorage with one or two percutaneous sutures, or gallbladder suspension with a needle grasper (Sreenivas et al, 2016).

Sutures are introduced in the abdominal cavity from a different site and the tissue is pierced, and then the sutures are retrieved through the abdominal wall. By pulling the thread outside, the tissue is retracted. Although some surgeons advocate this technique, it is cumbersome and sometimes causes bile spillage in laparoscopic cholecystectomy. Gadgets that measure 1.6-3 mm in caliber, including pre-tied loop, wire snare, and a needle grasper can be independently inserted elsewhere as in standard laparoscopic operations and used for tissue retraction (Toshiyuki et al, 2014).

There have been a number of modifications in the technique of laparoscopic cholecystectomy. Among them, a new technique utilizing a needle grasper held in the surgeon's left hand is developed. Two ports LC assisted needle grasper technique successfully reduce port numbers compared to conventional laparoscopic cholecystectomy while maintaining equivalent surgical outcomes in terms of

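### In both arms the written steps divide the cystic duct before the artery is cleared, and do not require the full critical view of safety before the first clip

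*Protocol*

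**What the plan says.** **The recommendation.** Section 1.1, repeated in section 2, presents bile duct injury as the serious complication to avoid and strongly recommends full exposure of the critical view before the cystic structures are clipped or divided. For operations with fewer or smaller ports it lists best practice to follow, including "identification and maintenance of the 'critical view' of the cystic duct and artery".

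**The definition.** Section 1.2 gives the view three elements: Calot's triangle dissected clear of fat and fibrous tissue; the gallbladder base separated from the cystic plate; and exactly two structures entering the gallbladder, each visible all the way round.

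**The operative steps.** In both arms the triangle is displayed and the cystic duct, cystic artery and both main ducts are identified (4.7.4 Step 4; 4.7.5 Step 5). The next step clears the duct all round, enters the triangle and then cuts the duct. For the conventional arm the wording is "Then cystic duct will be divided between haemoclips" (4.7.4 Step 5), and for the two-port arm "Haemoclips will be applied to cleared segment of cystic duct by 5 mm clip applier, and then cystic duct will be divided between haemoclips" (4.7.5 Step 6). The step after that reads, in the two-port arm, "The cystic artery will be identified and cleared of surrounding attachments" (4.7.5 Step 7; same wording in 4.7.4 Step 6). The gallbladder is taken off the liver one step later again. Section 4.7 does not mention the critical view anywhere.

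**The concern.** The protocol names one dissection standard as the way to keep bile duct injury low, and section 1.2 supports the grasper-assisted technique partly because it is reported to maintain that view. The operating instructions then set a written sequence that, if followed literally, reaches the first irreversible act (cutting the duct) before the standard is met. The hypothesis in section 3.3 is that the two-port method is as safe as the conventional one, and bile duct injury is a recorded outcome (4.7.8, 4.8.4). The instructions should therefore carry the safety standard that the rationale relies on. What is at stake is the safety of participants in both arms and the consistency of the document. The statistical comparison is not at stake.

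**Working it through.** There is no figure in the plan to reproduce. The check sets the step order beside the protocol's own definition.

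**Step order**

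| Action | 4.7.4 (CLC) | 4.7.5 (TPPOP LC) |
|---|---|---|
| Triangle displayed; duct, artery and main ducts identified | Step 4 | Step 5 |
| Duct cleared all round, triangle entered, duct divided between clips | Step 5 | Step 6 |
| Artery cleared, then divided | Step 6 | Step 7 |
| Gallbladder taken off the liver bed | Step 7 | Step 8 |

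Gap from duct division to artery clearance: 6 − 5 = 1 step in CLC and 7 − 6 = 1 step in TPPOP LC. The order is identical in the two arms.

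**The section 1.2 definition against what the text requires before the first clip**

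| Element | Required before the first clip? |
|---|---|
| Triangle freed of fat and fibrous tissue | In part: displayed and entered, with no instruction to clear it |
| Gallbladder base separated from the cystic plate | No: the text is silent on when, or whether, this is done |
| Exactly two structures, each seen all round | In part: 1 of 2 (the duct) is cleared all round; no two-structure check is stated |

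Tally: 0 of 3 in full, 2 of 3 in part, 1 of 3 not at all.

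**Is there a check before clipping?** The only verification wording in these steps is at the artery: "When this has been verified, the cystic artery will be divided in continuity between clips" (4.7.4 Step 6; 4.7.5 Step 7 has the same words). It comes after the duct has been divided and refers to the artery. The stated end of dissection before the duct is cut is that enough of the duct itself has been cleared.

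**Do the conversion rules fill the gap?** In part. Both respond to difficulty in identifying anatomy, but 4.7.6 names it together with moderate adhesions and inflammation, and 4.7.7 attributes it to dense adhesions and inflammation. Neither refers to the critical view.

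**The case against.** The best case for the plan has several parts.

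*The standard is background, not a rule.* The recommendation is cited literature that section 4 does not adopt, and the steps do not forbid the view. This stands as a limit. A reader might infer that surgeons in this trial will operate without the critical view. The documents do not support that, since a surgeon may obtain it in practice. The point is only that the written sequence does not ask for it.

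*The steps may not be strictly chronological.* The artery is said to be identified twice, first with the other structures and again in its own step, which suggests a structure-by-structure description. The figure cited at the duct-division step is captioned "Dissection of cystic duct and cystic artery", which fits artery dissection at that stage, and the figure itself is not available. This leaves real doubt about the artery and is why confidence is moderate. The caption does not mention the gallbladder base or a check before clipping.

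*Identification is already required.* The duct, artery and both main ducts are identified, and the duct is cleared all round, before any clip. That is substantial. Under the section 1.2 definition, however, the view is an end point of dissection, and identification alone does not reach it.

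*Late liver-bed dissection proves nothing about the base.* A reader might take the later step, "allowing the gallbladder to be dissected from the liver bed" (4.7.4 Step 7; 4.7.5 Step 8), as showing that the base is separated too late. It does not. That step is the complete removal of the gallbladder. On separation of the base the text is silent, and silence is all that can be claimed.

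*No consequence for the comparison.* This is correct. The order is the same in both arms.

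**Conclusion.** The point holds as a minor inconsistency that bears on patient safety, with moderate confidence. Followed as written, both arms divide the duct one step before the artery is cleared. Before the first clip, neither requires the base to be separated or two structures to be confirmed. This falls short of the protocol's own recommendation and definition.

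The conclusion assumes that the numbered steps are meant to be followed in order, and that the background recommendation is one the authors intend to apply to this trial.

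A reader might go on to infer a higher bile duct injury rate or a bias between arms. Neither follows. Section 1.3 cites injury rates of 1% to 2% for the conventional method and 1% to 3% for the two-port method, but nothing in the document relates these to step order. The sequence is common to both groups.

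**What to change.** Rewrite 4.7.4 Steps 5–6 and 4.7.5 Steps 6–7 so that, in both arms, the surgeon:

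1. clears the cystic duct and the cystic artery;
2. separates the gallbladder base from the cystic plate;
3. confirms that only two structures enter the gallbladder;
4. only then applies any clip and divides the duct and artery.

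Leave the full liver-bed dissection step where it is. Leave the conversion criteria in 4.7.6 and 4.7.7 unchanged as well. Making failure to obtain the view a new trigger would alter conversion, which is a study outcome (section 3.2, objective 3). It could do so unequally, because only the two-port arm can convert to the conventional method.

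The cost is the rewording of two short passages. Dissection may take slightly longer in some cases, which is expected to fall equally on both arms. Sample size and analysis do not change.

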4.7.6 Conversion to conventional laparoscopic cholecystectomy

Conversion to conventional laparoscopic procedure from TPPOP LC group will be performed where there are moderate adhesions and inflammation and difficulty to identify the important anatomy.

4.7.7 Conversion to open cholecystectomy

Conversion to open procedure from both study groups will be performed where there is difficulty to identify the important anatomy due to dense adhesions and inflammation, and complications such as bile duct injury, uncontrolled bleeding occurred.

4.7.8 Recording of parameters

The operation time will be recorded. Intraoperative complications including bile duct injury, bowel injury, vascular injury and injuries to nearby structures will be recorded. If conversion to other procedure from each group was present, it will be

recorded. Postoperative complications like prolonged ileus and wound infection will be recorded. Postoperative pain, rescue analgesic requirement and postoperative hospital stay will be recorded in the proforma.

4.7.9 Postoperative period

Nasogastric tube will be removed after operation. Antibiotics will be given single dose. If gallbladder perforation with bile spillage is present, antibiotics will be given total three doses.

For postoperative pain control, regular analgesic with paracetamol suppository (750 mg for <50 kg and 1 G for \geq 50 kg body weight of the patient) will be given 6 hourly up to 72 hours. The patient will be assessed the pain score by using visual analogue scale (VAS) within 12 hour, 24 hour, 36 hour and 48 hour. Rescue analgesia will be added with injection of intravenous tramadol 1mg/kg if VAS was more than 4 and/or if the patient suffers breakthrough pain or if the patient complain of pain between the assessments. Total number and dose of rescue analgesia will be recorded in the proforma.

Patient will be discharged according to discharge criteria. The postoperative hospital stay will be calculated and recorded in proforma for each patient. During the hospital stay all cases will be observed daily by the researcher for early postoperative complications till the patients are discharged from the hospital. The complications which will be observed are wound infection, prolonged ileus, bile duct injury and bowel injury. Complications will be diagnosed clinically and confirmed by relevant investigations. These complications will be recorded in the proforma. All the complicated cases will be treated under the experienced consultant surgeon together with the researcher. After resuming oral intake, oral cefixime 200 mg twice a day will be given up to 5th postoperative day. Patient will be ordered to take oral paracetamol 500 mg if they feel pain after discharge.

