1.3 Justification

Cholecystectomy is one of the most common elective operations in No.(1) Military Hospital (700 bedded) Pyin Oo Lwin. In 2018, 145 cholecystectomies were done (1/700 MH OT-Registry, 2018). Almost all cholecystectomies were done by conventional laparoscopic technique. Laparoscopic cholecystectomy has rapidly replaced open cholecystectomy as a standard treatment of symptomatic gall stones.

Conventional laparoscopic cholecystectomy is still gold standard procedure, but it still has chance of complications like wound infection, pain, bleeding and injury to nearby structures such as bile duct, bowel or liver. Among these injuries, bile duct injury is common and the percentage is 1% to 2%. The rate of open conversion from CLC is less than 1% (Sreenivas et al, 2016).

Two ports plus one puncture laparoscopic cholecystectomy is also acceptable procedure but it can carry longer operation. The percentage of bile duct injury is 1% to 3%. The conversion rate to conventional procedure is about 5.45% and to open procedure is about 0.18% (Sreenivas et al, 2016). Recent studies demonstrated two ports laparoscopic cholecystectomy using 2.3 mm alligator grasper has acceptable outcome. The main advantages of this two ports LC can be performed safely, principle as the previous conventional technique, reduce number of port, less painful, better for specimen delivery, higher cosmesis with shorter hospital stay (Nasir et al, 2018). Two ports laparoscopic cholecystectomy using conventional umbilical and epigastric ports assisted by 2.3mm alligator grasper may be the method of choice when considering laparoscopic cholecystectomy on a day-case basis due to early recovery.

Therefore, the key question about two ports plus one puncture laparoscopic cholecystectomy (TPPOP LC) is whether it provides a significant advantage over conventional laparoscopic cholecystectomy technique (CLC) now in use. There is no such comparative study in Military Hospitals and Myanmar yet.

So this study will compare the outcomes between conventional laparoscopic cholecystectomy (CLC) and two ports plus one puncture laparoscopic cholecystectomy (TPPOP LC). It may also help to find out safe and effective treatment options for symptomatic gallstones patients.

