3.2 Objectives

1. To compare the operation time between conventional laparoscopic cholecystectomy (CLC) and two ports plus one puncture laparoscopic cholecystectomy (TPPOP LC)
2. To compare the intraoperative complications of both study groups.
3. To compare the conversion rate of both study groups.
4. To compare the postoperative complications, postoperative pain, postoperative hospital stay of both study groups.

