4.8.15 Postoperative hospital stay

Duration of hospital stay means duration from the date of operation to the date of discharge according to discharge criteria.

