4.8.16 Discharge criteria

Patients will be discharged from the hospital when:

- (a) have no fever,
- (b) have no jaundice,
- (c) well tolerate to oral intake,

- (d) have recovery of bowel function,
- (e) can walk without assistance,
- (f) can manage postoperative pain with oral analgesic drugs and
- (g) no immediate postoperative complication.

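### Complications are counted only until discharge, so later wound infections are missed in both arms and the detection window is hospital stay, itself a compared outcome

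*Protocol*

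**What the plan says.** Protocol 4.7.9 sets the rule: all cases are "observed daily by the researcher for early postoperative complications till the patients are discharged from the hospital". The same section lists what is looked for: "The complications which will be observed are wound infection, prolonged ileus, bile duct injury and bowel injury".

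The end of that window is defined by another outcome. Section 4.8.15 measures stay as the "duration from the date of operation to the date of discharge according to discharge criteria", and the discharge criteria in 4.8.16 include "no immediate postoperative complication". Objective 4 in section 3.2 names both outcomes: "To compare the postoperative complications, postoperative pain, postoperative hospital stay of both study groups". Table 13 compares complications and Table 14 compares stay.

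For the time after discharge, 4.7.9 gives only an instruction about oral analgesia. The proforma (Appendix 1) has a discharge date and yes/no boxes for complications, with no onset date and no field for a later contact. The definition of wound infection in 4.8.13 has no time limit.

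**The concern.** A complication count is comparable between arms when every patient is watched for the same time. Here the watching time is the stay. Stay may respond to treatment, and in an open-label trial (4.1) the discharge decision is made knowing the arm. Because discharge requires the absence of an immediate complication, each window closes on a patient who is event-free at that moment. Anything that appears afterwards cannot enter Table 13.

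There are two consequences.

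- **Missed events in both arms.** This happens whether or not stays differ. It shrinks the counts and any true difference between them. The hypothesis in 3.3 is that the two-port technique is as safe as the conventional one, so lost events push toward the conclusion the trial hopes to reach.
- **Unequal observation, if stays differ.** Section 1.3 anticipates "higher cosmesis with shorter hospital stay" with the two-port technique. The arm that goes home earlier would then show fewer wound infections even if the true risk were identical.

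The protocol's own care continues past an early discharge: "oral cefixime 200 mg twice a day will be given up to 5th postoperative day", while the lowest band of Table 14 is 3 days or less. No analysis plan can recover events that were never collected.

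**Working it through.** **Arm size.** The plan's formula in 4.5 gives n = (1.96 + 0.84)² × (0.79² + 1.02²) / (2.85 − 2.31)² = 7.84 × 1.6645 / 0.2916 = 44.75. The plan states 44 (rounding up would give 45), and 44 / 0.9 = 48.9, hence 49 per arm and 98 in total. This size rests on analgesic need, not complications, and nothing below depends on the rounding.

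**Which outcomes are exposed.**

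- Prolonged ileus is judged by the third postoperative day (4.8.14), and discharge requires recovery of bowel function (4.8.16). It is settled before the window closes.
- Pain scores and stay do not use the complication window.
- Wound infection has no time limit and can appear after discharge. The same holds for a bile duct or bowel injury recognised late, since 4.7.9 lists both for postoperative observation.

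**Illustration for wound infection.** These inputs are assumptions, because the protocol gives none of them: the same true 30-day risk p in both arms (5% shown), lognormal onset time with log-SD 0.5 and median m of 3, 5, 7 or 10 days, and stays of 3 v 2, 7 v 4 or 2 v 2 days.

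- Share detected with stay s: F(s) / F(30), where F(t) = Φ(ln(t/m) / 0.5).
- Expected detected per arm: 49 × p × share.
- Apparent ratio: share in the shorter-stay arm divided by share in the longer-stay arm. The true ratio is 1.

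Example, m = 5, stays 3 v 2: F(3) = Φ(−1.02) = 0.153, F(2) = Φ(−1.83) = 0.033, and F(30) is essentially 1. The ratio is 0.22. True expected events are 49 × 0.05 = 2.45 per arm. Detected are 2.45 × 0.153 = 0.38 and 2.45 × 0.033 = 0.08. Missed: 4.90 − 0.38 − 0.08 = 4.44.

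| Stay (days) | Median onset | Detected, longer v shorter | Apparent ratio | Missed of 4.9 |
|---|---|---|---|---|
| 3 v 2 | 3 | 50% v 21% | 0.42 | 3.2 |
| 3 v 2 | 5 | 15% v 3% | 0.22 | 4.4 |
| 3 v 2 | 7 | 4.5% v 0.6% | 0.14 | 4.8 |
| 3 v 2 | 10 | 0.8% v 0.1% | 0.08 | 4.9 |
| 7 v 4 | 3 | 96% v 72% | 0.75 | 0.8 |
| 7 v 4 | 5 | 75% v 33% | 0.44 | 2.3 |
| 7 v 4 | 7 | 50% v 13% | 0.26 | 3.4 |
| 7 v 4 | 10 | 24% v 3% | 0.14 | 4.2 |
| 2 v 2 | 3 to 10 | equal | 1.00 | 3.9 to 4.9 |

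The ratio does not depend on p, and the missed counts scale with it.

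**Why equal loss still matters.** Suppose true risks of 10% and 5%, a stay of 3 days in both arms and median onset of 5 days. Expected events fall from 4.90 v 2.45 to 0.75 v 0.38. A difference of 2.45 events becomes one of 0.37.

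**With a fixed 30-day window**, the share is 100% in both arms and the apparent ratio returns to 1.00 under equal risk.

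**The case against.** The other side has several good points.

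- **A reader might infer that most wound infections are missed.** The documents give no onset time, rate or expected stay. With median onset at 3 days and stays of 7 v 4 days, 96% and 72% are caught, and Table 14 allows for stays beyond 14 days. Section 4.7.9 also plans rectal paracetamol up to 72 hours, so a 2-day stay may be uncommon.
- **A reader might infer that the two-port arm will be favoured.** That needs unequal stays. Section 1.3 expects a shorter stay, but sections 1.1 and 2 cite equivalent stay for the needle-grasper technique, and the discharge criteria are the same in both arms. With equal stays neither arm is favoured.
- **A reader might infer that objective 4 cannot be answered.** Pain, stay and prolonged ileus are untouched.
- **A reader might infer that suture removal supplies a ready contact.** The protocol says "All skin incisions will be closed with non-absorbable sutures", but describes no removal visit, date or place.
- **The scope is declared as early complications.** In part it is. Yet objective 4, definition 4.8.9 and Table 13 drop that limit, and even an early window should have the same length in both arms.
- **Follow-up may be described elsewhere.** The flow chart (Appendix 3) is not shown and the consent pages were removed, so this cannot be excluded. A follow-up step found only there would conflict with 4.7.9.

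The event numbers are also small, so a falsely significant P value is unlikely. The more realistic harm is false reassurance. What stands after all this is the fixed stopping rule and its two consequences, the second of them conditional.

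**Conclusion.** The concern holds in a limited form. Complication observation ends at discharge, so the detection window equals the stay, which is a compared outcome. Wound infections and late-recognised bile duct or bowel injuries that appear after discharge are lost in both arms, which makes the arms look alike and leans toward the hypothesis of equal safety. This requires only that some such events occur after discharge.

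If stays differ, the wound-infection comparison is also biased toward the shorter-stay arm. Under the assumed onset curves the apparent ratio lies between about 0.08 and 0.75 when the true ratio is 1, and it is 1.00 when stays are equal. These figures show direction and possible range. They do not predict this trial's result.

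**What to change.** In 4.7.9, the proforma and Table 13, count wound infection and the other complications over one fixed period from the day of operation in both arms, for example 30 days, whatever the discharge date. Record the onset date of each event and make one telephone contact at the end of the period.

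The cost is about 98 calls and one proforma section, and some patients will be unreachable; report their number by arm. Sample size and treatment do not change. The fix removes the unequal window but does not give power for safety: even with full capture, 49 per arm has about 15% power for 10% v 5%.

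If the sponsor keeps the in-hospital window, relabel the outcome as in-hospital complications in objective 4, 4.8.9 and Table 13, and limit the safety conclusion to that period.
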